14.1 BIOSTATISTICS

14.2 Sample Size

For each endpoint we will conduct three analysis:

- 1. A comparison of nightly sildenafil to PRN sildenafil with an alpha of 2.5%
- 2. A comparison of combination treatment to PRN sildenafil with an alpha of 2.5%
- 3. A non-inferiority comparison between nightly sildenafil and combination treatment: in this analysis, nightly sildenafil will be considered non-inferior to combination treatment if the upper bound of a 90% confidence interval for the difference between groups does not include combination treatment being at least three points superior to nightly sildenafil.

(RB PB

Amended: 02/12/13

- 15 -

IRB#: 09-005 A(10)

Our rationale is for the different comparisons is as follows. We want to know whether the two active arms (nightly sildenafil and combination treatment) are superior to control (PRN sildenafil). We will therefore test each against control using an alpha half of the conventional value to account for multiple testing. Furthermore, combination treatment, which involves penile injection, is less tolerable for patients than nightly sildenafil, which only involves oral medication. Therefore unless nightly sildenafil is demonstrably inferior to combination treatment, we will recommend that injections are not required. Hence we will conduct a non-inferiority comparison between the two active arms.

Our primary endpoint is the IIEF-EF at 24 months. Based on previous studies, we estimate that the SD for the IIEF-EF will be 9 points. Prior data at MSKCC suggest that the correlation between baseline and follow-up IIEF-EF will be small enough as to have a negligible effect on variance. The minimum, clinically significant difference between active and control arms is 6 points based on our clinical experience and discussion held with [name] the designer of the IIEF. If we obtain data from 80 patients on each of the two active arms (nightly sildenafil and combination therapy) and 40 patients on the control arm (PRN sildenafil), we will have 89% power for the comparison between active and control and 80% power for the non-inferiority comparison between active arms.

MSKCC surgeons do approximately 850 radical prostatectomies per year. We estimate that 50% of patients will be eligible for the study. Assuming that 25% - 33% of eligible patients enroll, we should complete accrual within 18-24 months.

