14.3 Data Analysis

Summary statistics will be calculated, by group, for age, surgery (open or laparoscopic), tumor characteristics (stage, grade, PSA), baseline erectile function and quality of life scores. Compliance and off-study use of medications for erectile function will be described by group and follow-up time. Biochemical recurrences will be described separately by group using Kaplan-Meier methods.

The primary analysis will compare the erectile function domain score of the IIEF at 24 months. Secondary endpoints include:

- 1. EF scores at other time-points
- 2. The proportion of patients who have normalization of their erectile function, defined as a score of 26 or greater on the EF domain of the IIEF at any point during the study
- 3. Time for response to sildenafil (as defined by diary)
- 4. Time to return of spontaneous functional erections (as defined by diary)

(RB PB

IRB#: 09-005 A(10)

The primary comparison and secondary comparison 1 will be made by analysis of covariance with baseline score and randomization strata as the covariates. Secondary endpoint 2 will be compared by Fisher's exact test. Secondary endpoints 3 and 4 will be compared between groups by log rank. Three pairwise comparisons will be made: nightly sildenafil vs. PRN sildenafil; combination treatment vs. PRN sildenafil; nightly sildenafil vs. combination treatment.

As an additional analysis, we will model EF scores over time using Generalized Estimating Equations with time, treatment, time by treatment and baseline score as predictors. Treatment will be entered as two dummy variables: nightly sildenafil (coded 0 in the PRN group and 1 otherwise) and injection therapy (coded 1 in the combination group and 0 otherwise).

All analyses will be on the intention-to-treat principle with patients analyzed in their randomized groups regardless of the treatment actually received. All comparisons between combination and PRN sildenafail, and between nightly and PRN sildenafil, will use a 2.5% alpha; all comparisons between the two treatment arms will use a 90% non-inferiority bound.

The nature, severity and day of onset of adverse effects will be described along with assessment of causality.

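### The stated 80% non-inferiority power fits a one-sided 90% bound with an undisclosed 10% error; the decision rule in 14.2, read as a two-sided 90% interval, gives about 68%

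*Combined protocol and SAP*

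**What the plan says.** Section 14.2 sets the criterion for comparing the two active arms. The condition for declaring nightly sildenafil non-inferior is that "the upper bound of a 90% confidence interval for the difference between groups does not include combination treatment being at least three points superior". The planning values are in the same section: SD 9 points on the IIEF erectile function domain, data from 80 patients on each active arm and 40 on control, and a baseline correlation that "will be small enough as to have a negligible effect on variance". The section then claims 89% power for each active-versus-control comparison and "80% power for the non-inferiority comparison between active arms".

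For the superiority comparisons, 14.2 describes "using an alpha half of the conventional value to account for multiple testing", which is 2.5% each. Section 14.3 says these "will use a 2.5% alpha; all comparisons between the two treatment arms will use a 90% non-inferiority bound".

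Neither section says whether the 90% is one-sided or two-sided, gives an alpha for the non-inferiority comparison, or states the true difference at which its power was calculated.

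**The concern.** A 90% confidence interval is by convention two-sided, and its upper limit leaves 5% in the tail. A one-sided 90% bound leaves 10%. With these arm sizes the choice moves the power by about 12 percentage points, and the stated 80% belongs to the reading that the wording of 14.2 does not ordinarily carry.

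The trial's recommendation on whether injections are needed rests on this comparison. If the reading is still open when the data arrive, an observed difference in a certain range can be reported as non-inferior or not, depending on which reading the analyst takes. Section 14.3 applies its bound to every comparison between the active arms, so the ambiguity is not confined to the primary endpoint.

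**Working it through.** **Inputs, all from 14.2:** SD 9; 80 per active arm; 40 on control; margin 3 points; superiority difference 6 points at alpha 2.5%; no variance reduction from baseline.

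**Assumption, not in the documents:** true difference between the active arms of 0, the usual planning choice. Other values are shown below.

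**Check of the inputs against the 89%.**
- SE = 9 × √(1/80 + 1/40) = 1.743, and 6/1.743 = 3.442.
- Two-sided 2.5%: Φ(3.442 − 2.241) = 88.5%, which agrees with the stated 89%.
- One-sided 2.5%: Φ(3.442 − 1.960) = 93.1%, which does not.
- So the SD and arm sizes are the ones the authors used, and the superiority figure is two-sided.

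**Non-inferiority power.** SE = 9 × √(2/80) = 1.423, and 3/1.423 = 2.108. Power = Φ((3 − δ)/SE − z), where δ is the true advantage of combination treatment.

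| True advantage of combination (δ) | Two-sided 90% interval (5% one-sided error, z = 1.645) | One-sided 90% bound (10% one-sided error, z = 1.282) |
|---|---|---|
| 0 | 67.8% | 79.6% |
| 0.5 | 54.5% | 68.3% |
| 1 | 40.5% | 54.9% |

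At δ = 0 the noncentral t with 158 degrees of freedom gives 67.5% and 79.4%, so the normal approximation is not the cause of the gap.

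**Could the two-sided interval still give 80%?**
- By a favourable true difference: 3 − (1.645 + 0.842) × 1.423 = −0.54. Nightly sildenafil would have to be about 0.54 points better, and no such assumption is stated.
- By covariate adjustment: the effective SD would have to be 3 / [(1.645 + 0.842) × √(2/80)] = 7.63. That needs a baseline correlation of √(1 − (7.63/9)²) = 0.53, which conflicts with the negligible effect stated in 14.2.
- By sample size: 2 × 81 × (1.645 + 0.842)² / 9 = 111.3, so about 112 per arm with data.

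**Where the verdict changes.** The largest observed advantage of combination treatment that still passes is:
- two-sided 90% interval: 3 − 1.645 × 1.423 = 0.66;
- one-sided 90% bound: 3 − 1.282 × 1.423 = 1.18.

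The probability that the observed difference falls between 0.66 and 1.18 is 0.117, 0.144 and 0.108 at true advantages of 0, 1 and 2 points.

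**The case against.** The strongest reply is that the 80% is not a miscalculation. It reproduces from the plan's own inputs under a reading the text permits. Non-inferiority is a one-directional question, only the upper limit enters the rule, and 14.3 speaks of a 90% bound. A two-sided superiority test beside a one-sided non-inferiority test is normal practice. A lenient error rate could also be deliberate, since 14.2 argues that injections are less tolerable and should have to earn their place. Finally, the readings disagree only in a band about half a point wide, so at the true differences examined the verdict is the same in roughly 86% to 89% of trials.

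Much of this stands. The 80% and the wording of 14.3 do favour the one-sided bound, a 10% one-sided error is a legitimate choice if declared, and the two-sided 89% does not show which 90% was meant. But the rule itself, in 14.2, is framed as a confidence interval, and nothing elsewhere overrides the usual meaning. A reader has to work backwards from the power to find the error rate. If that inference is right, the error at the margin is twice what the ordinary reading implies, and the plan does not say so.

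**Conclusion.** The concern holds. Applied in the ordinary way, the rule in 14.2 has about 68% power, not 80%. The 80% requires a one-sided 90% bound with a 10% one-sided error that is not stated anywhere in the plan. This is a mismatch between the decision rule and its stated power, with the sidedness left open; it is not a slip in the arithmetic.

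The power figures rest on the plan's SD of 9, 80 patients per active arm with data, no gain from baseline adjustment, and an assumed true difference of 0. The 12-point gap at zero becomes about 14 points if combination treatment is truly 0.5 or 1 point better. The cut-offs of 0.66 and 1.18 do not depend on the assumed true difference. This should be fixed, but it does not invalidate the design.

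**What to change.** In 14.2 and 14.3, use the same words for the non-inferiority criterion. State whether the 90% is one-sided or two-sided, give the one-sided alpha, and give the true difference at which power is calculated. Then choose one of two courses before the data are seen:

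- keep the two-sided 90% interval (5% one-sided error) and restate the power as about 68% at a true difference of 0; or
- declare a one-sided 90% bound, keep the 80%, and disclose the 10% one-sided error.

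The cost is a change of wording in two sections, plus either a less favourable power figure or an openly higher error rate. Neither course needs more patients or alters the margin, the data collected or the superiority comparisons.

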14.3 Data Analysis

Summary statistics will be calculated, by group, for age, surgery (open or laparoscopic), tumor characteristics (stage, grade, PSA), baseline erectile function and quality of life scores. Compliance and off-study use of medications for erectile function will be described by group and follow-up time. Biochemical recurrences will be described separately by group using Kaplan-Meier methods.

The primary analysis will compare the erectile function domain score of the IIEF at 24 months. Secondary endpoints include:

- 1. EF scores at other time-points
- 2. The proportion of patients who have normalization of their erectile function, defined as a score of 26 or greater on the EF domain of the IIEF at any point during the study
- 3. Time for response to sildenafil (as defined by diary)
- 4. Time to return of spontaneous functional erections (as defined by diary)

(RB PB

IRB#: 09-005 A(10)

The primary comparison and secondary comparison 1 will be made by analysis of covariance with baseline score and randomization strata as the covariates. Secondary endpoint 2 will be compared by Fisher's exact test. Secondary endpoints 3 and 4 will be compared between groups by log rank. Three pairwise comparisons will be made: nightly sildenafil vs. PRN sildenafil; combination treatment vs. PRN sildenafil; nightly sildenafil vs. combination treatment.

As an additional analysis, we will model EF scores over time using Generalized Estimating Equations with time, treatment, time by treatment and baseline score as predictors. Treatment will be entered as two dummy variables: nightly sildenafil (coded 0 in the PRN group and 1 otherwise) and injection therapy (coded 1 in the combination group and 0 otherwise).

All analyses will be on the intention-to-treat principle with patients analyzed in their randomized groups regardless of the treatment actually received. All comparisons between combination and PRN sildenafail, and between nightly and PRN sildenafil, will use a 2.5% alpha; all comparisons between the two treatment arms will use a 90% non-inferiority bound.

The nature, severity and day of onset of adverse effects will be described along with assessment of causality.

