2.1 OBJECTIVES AND SCIENTIFIC AIMS

The objective of this study is to analyze the ability of 3 different pharmacological strategies to preserve the ability of men to achieve spontaneous (non-medication assisted) functioning erections after bilateral nerve-sparing radical prostatectomy.

Primary End-Point: Difference in the erectile function (EF) domain score of the International Index of Erectile Function (IIEF) between the 3 groups at 24 months.

Secondary End-Points:

- The time to return of spontaneous functional erections
- The time for patients to respond to oral erectogenic therapy
- The proportion of patients who have normalization of their erectile function (normalization of the EF domain of the IIEF)

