Sildenafil citrate (Viagra) enhances the effects of nitric oxide (NO), a signaling molecule that has a diverse range of physiological effects in many tissues, including promoting relaxation of smooth muscle in the walls of blood vessels and the erectile tissue within the corpora cavernosa of penis. The effect of NO on smooth muscle is mediated by cyclic guanosine monophosphate (cGMP); sildenafil works by inhibiting the enzyme, cGMP-specific phosphodiesterase type 5 (PDE5), that degrades cGMP. Experience has established the role of sildenafil citrate in the treatment of erectile dysfunction (ED). The efficacy of sildenafil for ED post-radical prostatectomy has been studied. In the seminal publication by Goldstein et al, subpopulation analysis suggested a 43% responder rate (GAQ positivity) for this population. Since then in numerous prostatectomy specific studies, sildenafil has been identified as a useful management strategy to facilitate men resuming sexual relations.

A recent Pfizer sponsored study assessed the utility of daily sildenafil citrate administration on the recovery of spontaneous erectile function after radical prostatectomy. In a randomized fashion, 25 men were treated with 50 mg daily, 25 with 100 mg daily and 25 were treated with

IRB PB

IRB#: 09-005 A(10)

placebo. Therapy was instituted at 4 weeks postoperatively and lasted 38 weeks. Analysis was conducted at 48 weeks following RP. The criteria for inclusion were rigorous, patients requiring a combined score of 8 from questions 3 and 4 on the IIEF questionnaire as well as at least one 55% erection on nocturnal penile tumescence and rigidity analysis. Success was defined as preservation of the score of 8 on questions 3 and 4 of the IIEF. No difference was seen in the success rate between the 50 mg and 100 mg arm of the study. However, 27% of men in the treatment arm compared to 4% of men in the placebo arm had preservation of preoperative erectile function. While cavernosal oxygenation may be a contributor to these results, most of these patients did not obtain an erection in response to sildenafil early postoperatively, thus other factors must be at play.

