The relationship between hypoxia and cavernosal fibrosis has been documented in several studies (11), it is thought that hypoxia induces TGF-beta1 that in turn accelerates collagenization of the corpus cavernosum smooth muscle, while at the same time, decreasing the level of PGE1 that help protect from fibrosis (12). Since, hypoxia of cavernous tissue is related to the blood supply and the greatest blood supply occur at time of erection any neural damage that results in ED may expose the cavernous tissues to longer periods of hypoxia. Leungwattanakij et al (13) demonstrated in a cavernous neurotomy rat model that sharp neural injury resulted in an increase in hypoxia inducible factor-1 (HIF-1alpha) and TGF-beta1 as well as increase in cavernous tissue collagen synthesis. In a landmark study, Montorsi et al (5) based a study on the assumption that the events of nocturnal erection supply the cavernous bodies with oxygenation that might protect them from developing fibrotic changes during the transient period of erectile dysfunction following nerve sparing radical prostatectomy. In their study they treated patients with 3 weekly intracavernousal injections of Alprostadil. This in

IRB PB

IRB#: 09-005 A(10)

turn would ensure that when the erectile function would resume the secondary fibrotic changes to the penile tissue would not be sever enough to cause erectile dysfunction on their own. In this prospective study 30 patients were enrolled, all potent, all had nerve-sparing RP. 15 received 3 weekly injections for 15 weeks. 12 completed the treatment. Although the trial was small, the difference between treatment and control group was statistically significant. (Treatment group - 67% had erections sufficient for intercourse versus. 20% in the Control group - p < 0.01) However, to date this is the only randomized evidence supporting the role of penile rehabilitation with intracavernosal injections after radical prostatectomy. There is a need for a larger confirmatory study particularly using a modality that avoids intracavernosal injections. Intracavernosal injection therapy was originally discovered in 1983. In 1985, trimix, in the form of papaverine/phentolamine/prostaglandin E1 was introduced. It is efficacious in approximately 90% of patients with ED.

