4.1 OVERVIEW OF STUDY DESIGN/INTERVENTION

4.2 Design

Patients undergoing either laparoscopic or open nerve-sparing radical prostatectomy, who meet the inclusion and exclusion criteria described in section 6.0, will be asked to participate in the study. Patients will be randomized into one of three arms and assigned a study number from CRDB (unrelated to their medical record number):

- life according to their ability; patients interested in using medication for sexual activity, will be offered sildenafil 100 mg to be used before intercourse on an asrequired basis. They will be given six 100 mg doses, per month, for a 12 month duration. Each patient in this group will use a placebo pill (blinded) each night, except on a night that 100 mg is taken for the purpose of sexual relations. This group can be considered to constitute "usual care" as it represents the current approach to penile rehabilitation in the community. We estimate, in the first 3 months, most people will not use sildenafil at all, after this, probably no more than once per week on average. The total expected dose in the PRN group is about 4000 mg over the course of the year. There will be 40 patients in this group.
- 2. Nightly Sildenafil Arm: Patients will be instructed to take sildenafil 50 mg (blinded) at night regularly, even when intercourse is not planned. These patients will be instructed to take 100 mg pill on occasions that they are interested in sexual relations. On these occasions, they will forego the usual nightly pill. They will be given six 100 mg doses, per month, for a 12-month duration. There will be 80 patients in this group.
- **3.** Combination Therapy Arm: Intracavernous injections of a trimix combination (Papaverine 30 mg/mL, Phentholamine 1 mg/mL, Prostaglandin E1 10 mcg/mL) will be injected three times a week, and sildenafil 50 mg taken on the other four

IRB PB

IRB#: 09-005 A(10)

(non-injection) nights. Injection therapy can be used for the purpose of sexual relations. There will be 80 patients in this group.

Preoperative consent: Patients will be evaluated in the clinic and will complete the questionnaires at baseline (before surgery) and 3, 6, 9, 12, 18 and 24 months after surgery. At 12 months postoperatively, all patients will stop treatment. Visits 3, 6, 9, 12, 18, and 24 months will have ± 2 week window.

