4.3 Blinding

Preoperative consent: Patients are to be consented and registered as pending prior to their surgery. Full registration and randomization will occur immediately following surgery, if nerve bundles have been spared.

Postoperative consent: Patients may also consent to the study up to 6 weeks postoperatively at which point they will be registered and randomized immediately following informed consent in clinic.

The blind 50 mg pills will be taken last thing at night, before the patient goes to bed without sexual stimulation (100 mg will be used for sexual relations). Thus, the chances of a man having an erection that would "unblind" him is remote. Furthermore, in the first 9 months after surgery, very few men will respond to any PDE5 inhibitor medication because of the intra-operative transient nerve injury. Finally, it takes on average, one hour before an erection can occur, and this must be in the setting of sexual stimulation. Thus, the patient will likely be asleep at this time. Hence, we believe that patients will remain blinded to whether they are on active or placebo sildenafil. Nonetheless, blinding will be assessed at the end of the study.

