4.4 Intervention

Three interventions are to be used:

1. PRN Sildenafil Arm: Patients will be instructed to take placebo QHS (blinded) except on nights that they are interested in sexual relations, they will then be instructed to use sildenafil 100 mg (open-label) and skip the placebo dose. Placebo will start within 24-48 hours after registration. There will be 40 patients in this group.

(RB PB

IRB#: 09-005 A(10)

- 2. Nightly Sildenafil Arm: Patients will be instructed to take sildenafil 50 mg QHS (blinded) except on nights that they are interested in sexual relations, they will then be instructed to use sildenafil 100 mg (open-label) and skip the 50 mg dose. Sildenafil treatment will start within 24-48 hours post-surgery. There will be 80 patients in this group.
- 3. Combination Therapy Arm: Trimix combination (Papavarine 30 mg/mL, Phentholamine 1 mg/mL, Prostaglandin E1 10 mcg/mL), at initial dose of 5 units (0.05 mL) will be given; the first 2 injections will be done in the MSKCC urology outpatient clinic (if needed, the investigator can determine appropriate amount of injections for patient training). The patients will be instructed, by the sexual medicine nurse practitioner, on the technique of injection and dose titration, as well as the limitations, contra-indications, side effects and alternatives. The dosing data will be entered into electronic medical record or patient medical record by the NP. The dose being used cannot be altered by a patient. For safety reasons all dose adjustments are conducted by phone with the NP.

For the first 2 weeks after registration, patients will use nightly sildenafil 50 mg before commencing penile injections 2 weeks (± 3 days) later. Sildenafil treatment will start within 24-48 hours after registration. Patients will inject three times per week and use sildenafil 50 mg on the other four nights. In this arm, patients will be instructed to obtain 3 penetration hardness ($\geq 60\%$ rigidity) erections per week. There will be 80 patients in this group.

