9.0 TREATMENT/INTERVENTION PLAN

Patients will be randomized into one of 3 arms as described above, and will be followed up for 24 months. Patients will be encouraged to have sexual relations, when comfortable after RP. This is 'usual care'. The use of nightly sildenafil citrate and intracavernosal injection therapy is considered investigational, and this study is designed to define whether one, or the other, or a combination of these strategies, should become 'usual care'. Patients routinely complete questionnaires after surgery, the only additional requirement for patients will be the completion of a pill diary/sexual encounter diary, to delineate the exact utilization of medication for sexual relations as well as document all study medication use. Patients will be followed at 3, 6, 9, 12, 18, and 24 months. Intervention (placebo, sildenafil or injection) will be used for 12 months. Patients will have their sildenafil dose adjusted according to their erectile response and side effects (listed in section 11.0). For example, for men responding robustly to sildenafil 100 mg may be down-titrated to 50 mg or 25 mg. Likewise, men who have side effects (as outlined in Section 11.0) at sildenafil 100 mg will be down-titrated to 50 mg or 25 mg. If patients are experiencing side effects from daily 50 mg dose, they may downtitrated to 25mg, by halving the pill. Intra-cavernosal injection agent dose will be downtitrated for penetration hardness erection lasting for greater than 60 minutes or if any side effects are seen, as listed in section 11.0. Trimix and Bimix have a 1 month expiration date. Combination Therapy Arm patients will be prescribed a total of 3 vials of Trimix or Bimix at their 2nd injection training visit and 3, 6, and 9 month protocol visits. The patient will pick up 1 vial after their appointment and outpatient pharmacy will arrange to have the remaining 2 vials shipped to the patient at 1 month intervals to cover their treatment plan for a total of 3 months.

IRB PB

IRB#: 09-005 A(10)

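### Normalization (secondary endpoint 2) accepts scores from on-treatment visits, so trimix-assisted function can count in favour of the combination arm

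*Combined protocol and SAP*

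**What the plan says.** The objective in section 2.1 is to "preserve the ability of men to achieve spontaneous (non-medication assisted) functioning erections". The same section lists normalization of the EF domain as a secondary endpoint, without a time point or a condition on drug use. Section 14.3 supplies the definition: "defined as a score of 26 or greater on the EF domain of the IIEF at any point during the study". It is compared pairwise by Fisher's exact test, at an alpha of 2.5% for each active arm against PRN.

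The IIEF is completed at baseline and at months 3, 6, 9, 12, 18 and 24 (section 10.0). On treatment length, section 9.0 says: "Intervention (placebo, sildenafil or injection) will be used for 12 months".

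For the combination arm, section 4.2 says: "Injection therapy can be used for the purpose of sexual relations". Section 4.4 adds a weekly target: "In this arm, patients will be instructed to obtain 3 penetration hardness" erections. The other two arms have open-label sildenafil 100 mg for intercourse. After month 12, section 10.0 lets men in any arm use sildenafil or injections for sex, prescribed by their own physician.

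On drug response, section 3.0 says of trimix: "It is efficacious in approximately 90% of patients with ED". For sildenafil after prostatectomy it cites a trial in which "subpopulation analysis suggested a 43% responder rate (GAQ positivity) for this population". Section 4.3 states that "in the first 9 months after surgery, very few men will respond to any PDE5 inhibitor medication".

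**The concern.** One qualifying score at any visit is enough, and nothing in the visible text limits scores to unassisted erections or sets aside scores obtained on study drug. During months 3 to 12 the strongest erectogenic aid is assigned to one arm only. On the protocol's own account that aid works in most men with ED, while the oral drug open to the other arms works in very few men for the first 9 months after surgery. A combination man can thus be counted as normalized because of his injections, where a man with the same underlying recovery in another arm would not be.

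What is at stake is the interpretation of one formally tested secondary endpoint. Combination could appear better than PRN without better recovery of natural function, and the combination-minus-nightly difference would shift in the same direction. Nightly against PRN should be much less affected, though not wholly unaffected, because nightly men also take active 50 mg.

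The definition has a second looseness. Section 6.2 admits men with a baseline EF score of 22 or more, so some will already score 26 or more at entry. Read literally, those men meet the endpoint before treatment, which would dilute every comparison.

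**Working it through.** **Plan's own figures.** The documents give no rate, power or margin for endpoint 2, so there is none to reproduce. The primary-endpoint power does show how the 2.5% alpha is meant. With SD 9, difference 6, and 40 v 80 men, the standard error is 9 × √(1/40 + 1/80) = 1.743. Then 6/1.743 = 3.443, less 2.241 (two-sided 2.5%) gives 1.201, and Φ(1.201) = 88.5%, against the stated 89%. The check below therefore uses a two-sided 2.5%.

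**Visits.** Post-baseline IIEF visits: 3, 6, 9, 12, 18, 24. With 12 months of treatment, 4 of 6 lie within it or at its end.

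**Model, assuming no true difference in recovery.**
- b = share who reach 26 in any case, equal in both arms. Assumed 30%, varied from 20% to 50%.
- Trimix response 0.90 and sildenafil response 0.43 (section 3.0). Neither is a rate of EF ≥ 26.
- f = share of drug responders who reach 26 only on drug. Assumed 10%, 25% or 50%, the same for both drugs.
- Combination: p = b + (1 − b) × f × 0.90.
- PRN: p = b + (1 − b) × f × 0.43.

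The rejection probability of Fisher's exact test (two-sided p ≤ 0.025, 80 v 40) comes from summing over all binomial outcomes. With no excess and b = 30%, it rejects in 2.0% of trials.

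| f | Combination (b = 30%) | PRN (b = 30%) | Net excess | Rejects |
|---|---|---|---|---|
| 10% | 0.30 + 0.70 × 0.10 × 0.90 = 0.363 | 0.30 + 0.70 × 0.10 × 0.43 = 0.330 | 3 points | 2.7% |
| 25% | 0.30 + 0.70 × 0.25 × 0.90 = 0.458 | 0.30 + 0.70 × 0.25 × 0.43 = 0.375 | 8 points | 7.3% |
| 50% | 0.30 + 0.70 × 0.50 × 0.90 = 0.615 | 0.30 + 0.70 × 0.50 × 0.43 = 0.451 | 16 points | 24.8% |

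Over bases of 20% to 50%, f = 25% gives 4% to 9% and f = 50% gives 16% to 35%.

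**What the model leaves out.** Men in the PRN and nightly arms who reach 26 with an aid at month 18 or 24 also count. That lowers the net excess. The documents give no figure for such use, so the table stands before this offset.

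**If baseline scores counted.** The base would be higher in all arms. At assumed bases of 70% to 90%, with f = 50%, rejection is only 3% to 8%; real differences would be compressed in the same way.

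**The case against.** The best defence is that endpoint 2 was never meant to be unassisted. Section 2.1 labels only the return of erections as spontaneous; its neighbour, response to oral therapy, is drug-assisted by nature. Spontaneous recovery has its own diary endpoint, tested by log rank, and EF scores are also compared visit by visit. On that reading endpoint 2 means having reached normal function at some time, by whatever means. This has weight, but the section does not state that reading and its overall objective points the other way. The neighbouring endpoints help a reader interpret the result; they do not alter the endpoint 2 test.

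The offsets are also real. Sildenafil-assisted scores count in the other arms, increasingly by month 12, and any aid counts in every arm after that. They shrink the excess. The documents do not show that they remove it.

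Appendix A is listed by title only. If the form tells men to answer for unassisted erections, the concern is largely resolved.

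A reader might instead infer a much larger effect by treating the early sildenafil response as, say, 10%, which would take rejection as high as 71% at f = 50%. The documents do not support that: the statement in section 4.3 covers only the first 9 months, whereas the endpoint accumulates over 24. Nor does 90% trimix efficacy mean that 90% would score 26 or more.

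**Conclusion.** The concern holds as a matter of definition and direction: as written, the endpoint can credit drug-produced function to the combination arm more often than to the others. Its size cannot be fixed from the documents. Under the stated assumptions, and before the offset after month 12, the test against PRN rejects in about 3% of trials if few drug responders reach 26 only on drug, and in about 25% if half do, compared with 2% when there is no excess. The base rate, the share f and its equality for both drugs are assumptions.

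Two wider conclusions might be inferred and are not supported. The primary endpoint does not share this on-treatment problem, because month 24 comes a year after assigned treatment ends. No effect on the recommendation about injections is shown either: the three-point margin in section 14.2 is in EF points, and no margin is given for a proportion.

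**What to change.** In section 14.3:
- Define normalization for the Fisher test as an IIEF-EF score of 26 or more at month 24, with month 18 supportive.
- Report the proportion reaching 26 at any post-baseline visit descriptively, by visit and arm. This also closes the baseline gap.
- Add a sensitivity analysis in which a man is normalized only if he scores 26 or more and his diary for that visit records no aid. Keep all randomized men in the denominator and count aid users as not normalized. It should remain a sensitivity analysis, because aid use is decided after randomization.
- Check whether Appendix A already asks men to rate unassisted erections and, if so, say so in the definition.

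This is a wording change that uses IIEF and diary data already scheduled at months 18 and 24. The costs are fewer events, dependence on month 24 attendance, overlap with the primary endpoint, and some assisted scores remaining in the main definition.

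As an illustration of the power cost, take an assumed true difference of 30% v 55% (80 v 40, alpha 2.5%), with power 62%. If 10% of normalized men in each arm lose it by month 24, the rates become 0.30 × 0.9 = 27% and 0.55 × 0.9 = 49.5%, and power is 53%. If 10% also miss the visit (72 v 36), it is 48%.
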